they must not have missed more than 1 exercise session per week to receive the finishing bonus. In the case that a participant anticipates being unable to attend one or more of the exercise training sessions, the participant will have the opportunity to work out on his or her own if he or she informs the trainer ahead of time. The trainer will then provide the participant with "homework" and a training log. The homework will describe the exercise the participant should do while away. The participant will be reminded that he or she will need access to exercise training equipment. The trainer will instruct the participant in how to fill out the training log. We may ask the participant to wear a heart rate monitor or activity monitor or similar device during the exercise. We will provide this device to them. A study staff member may call them about their training progress while they are away. Participants will be expected to return the training log to the trainer after their return. Participants will not have the opportunity to receive homework during the first four weeks of the exercise training program. This is for the safety of the participants, given that the trainers will monitor their progress and instruct them in proper technique during the first four weeks. If a participant anticipates being unable to participate during this time, we may exclude him or her from participating in this study or place him or her on a waiting list. A participant will not necessarily be excluded if he or she is not available for the duration of the study, unless the participant anticipates that he or she will miss any of the study visits (study visits 1, 2, 3, 40, 41) and/or if he or she anticipates missing three exercise sessions in a row without fulfilling the homework and training log requirements. Make-up sessions during the same week will also be available.

Exercise diary/log. We will ask the participants to continue using the exercise diary/log until the study is completed. We will go over the exercise diary with the participant on approximately a weekly basis.

5) Study Visit 40: Follow-up fitness testing and body composition exam

Duration: Approx. 2-2.5 hours

Location: BU Fitness and Recreation Center

Procedures: Procedures are identical to Study Visit 2.

6) Study Visit 41: Follow-up MRI exam

Duration: Approx. 4 hours

Location: Cognitive Neuroimaging Center at Boston University Charles River Campus

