Measurements: upper body strength in lbs or kg (based on chest press and latissimus dorsi pulldown), lower body strength in lbs or kg (based on leg press)

3) Increased lean body mass

Measurements: Percent lean body mass from BIA (and/or skinfold measures)

4) Neuropsychological test performance: improved performance scores on tests of spatial cognition, verbal memory, visuo-spatial memory, visuo-spatial attention, and executive functions post-exercise training compared to baseline and compared to controls

Measurements: neuropsychological test scores

Data Analysis

Provide a description of your plan for data analysis. State the types of comparisons you plan (e.g. comparison of means, comparison of proportions, regressions, analysis of variance). Which is the PRIMARY comparison/analysis? How will the analyses proposed relate to the primary purposes of your study? If you are doing qualitative research please state how comparisons will be made.

Specific Aim #1:

Behavioral and Fitness Data Analysis. The primary measures for the primary cognitive task (Sternberg memory load task) are % correct and reaction times, and for fitness are estimated VO 2 max. The primary statistical analyses will be repeated-measures ANOVAs with the factors group (aerobic vs. control) and time (pre vs. post) to examine group x time interactions on the outcome measures. Posthoc tests (e.g. Tukey tests) will examine if a significant group x time interaction is due to a greater improvement post-intervention in the aerobic exercise group compared to controls. Dependent measures will be tested for normality and skewed data log-transformed. We will use an alpha of 0.05, corrected for multiple comparisons.

Univariate fMRI and Functional Connectivity Analyses. We will use SPM8 and related software for statistical analysis of fMRI data. We will estimate voxel-based Statistical Parametric Maps (SPMs)

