and compare them between and within groups with mixed-design ANOVAs. We will use baseline fitness as a covariate. Because the entorhinal cortex and the hippocampus are our primary brain regions of interest, we will use a seed-based functional connectivity approach. We will compare task-related functional connectivity: 1) pre versus post intervention, and 2) aerobic exercise versus control. We will use the psycho-physiological interaction (PPI) approach91 using the Generalized PPI Toolbox92 for SPM8. The time course from a seed region constitutes the physiological variable, and the contrast of interest (e.g. high memory load > low memory load) constitutes the psychological variable in the PPI model. Our search space will be restricted to the medial temporal lobe region. We will determine the PPI variable by calculating the voxel-wise product between the physiological and the psychological variables. We will also correlate SPMs and functional connectivity strength with cognitive test scores. Analyses will include nuisance regressors (e.g. head motion).

Specific Aim #2:

Data Analysis. See Aim #1. The behavioral outcome variables of the primary cognitive task (allocentric navigation task) are distance traveled and movement speed. Addicional outcome variables are neuropsychological test scores and spatial reasoning test scores. Analyses will be as described for Specific Aim #1. In addition, we will compare two groups that differ in relative EC volume or path integration ability (by median split) using descriptive statistics (means, confidence intervals) due to the exploratory nature/ small sample size.

Sample Size

Sample Size Justification

Approximately 94 participants will be recruited total for the study: For the exercise training program

/study intervention, approximately 84 participants will be recruited with the aim to enroll 42 participants, 21 per group; for the cognitive and fMRI pilot studies, an additional 10 participants will be recruited with the aim to enroll 5 participants in the cognitive pilot and 5 participants in the fMRI pilot. Thus, this totals 94 participants (84 + 5 + 5 = 94) required to complete the cognitive pilot, fMRI pilot, and exercise training program/study intervention.

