For the exercise training program/study intervention, the sample size for enrollment was determined from simulation-based power predictions for fMRI (Desmond & Glover, 2002), and based on a metaanalysis on exercise training effects on cognition in older adults (Colcombe and Kramer, 2003). 1) fMRI: Given an estimated mean difference of 0.5% signal change, a between-subject variance of 0.5%, and a statistical power of 0.80, a sample size of 11-12 subject per group would be needed for $\alpha = 0.05$ and N = 21 per group for $\alpha = 0.002$. 2) Cognition: we performed sample size calculations with G*Power 3.1.7 based on effect sizes reported in the literature. Effect sizes were f = 0.26 for a short-duration exercise intervention, f = 0.30 for session durations of 45 min, f = 0.20 for cardiovascular training only, f = 0.21 for the visuospatial domain, and f = 0.35 for participants aged 65+ years. Based on an average f of 0.26, a statistical power of 0.80, and alpha = 0.05, a total N = 32 subjects will be needed. Oversampling to 42

Risks and Benefits

Risks associated with the cardiovascular fitness and strength tests

The exercise test will require a gradual increase of exercise intensity. Because it is very strenuous to reach maximum oxygen uptake even after rest it may pose a health risk for some participants. Risks and discomforts include the possibility of adverse changes during the test, including abnormal blood pressure, fainting, dizziness, severe fatigue, body aches, heart rhythm abnormalities, stroke, and very rare instances of heart attack.

Risks and discomforts associated with the strength tests include feeling tired and experiencing muscle cramps. Other, less common, risks and discomforts include muscle tear, spraining a ligament (connective tissue) and lightheadedness.

Risks associated with bioelectrical impedance analysis (BIA)

The bioelectric impedance analysis (BIA) uses a very small electrical current, which passes between electrodes placed on the hands and/or feet. The amount of this current is slight enough that the participants will not be able to feel it and poses no risk to humans. However, there is a slight risk that this low current could disrupt an artificial pacemaker or defibrillator.

Risks associated with exercise

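### The pre/post repeated-measures ANOVA compares change among participants with both visits; a baseline-adjusted analysis of everyone randomised would be more precise and less exposed to bias from loss to follow-up

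*Combined protocol and SAP*

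**What the plan says.** Under Data Analysis, Specific Aim #1 (Behavioral and Fitness Data Analysis), the protocol states: "The primary statistical analyses will be repeated-measures ANOVAs with the factors group (aerobic vs. control) and time (pre vs. post". The group x time interaction is the test of interest for the Sternberg task measures and estimated VO2max. The error rate is set out as "We will use an alpha of 0.05, corrected for multiple comparisons". Specific Aim #2 adopts the same analyses for its behavioural outcomes.

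Baseline fitness is a covariate in the fMRI models. No baseline covariate is named for the behavioural and fitness models. The text supplied gives no analysis population, no rule on analysing participants as assigned, no missing-data method and no sensitivity analysis.

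The Sample Size Justification says, for cognition, "Based on an average f of 0.26, a statistical power of 0.80, and alpha = 0.05", and then "a total N = 32 subjects will be needed". It continues "Oversampling to 42", where the available text breaks off. The enrolment target is set "with the aim to enroll 42 participants, 21 per group". The fMRI calculation in the same section also arrives at 21 per group, at alpha 0.002.

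The section on Study Visits 4-39 says that limited availability need not exclude a person, with exceptions. One is expecting to miss a study visit; another is "if he or she anticipates missing three exercise sessions in a row without fulfilling the homework and training log requirements". The 30-of-36 attendance threshold there is a condition for the finishing bonus only.

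**The concern.** With one pre and one post measurement, the interaction F test is the square of a two-sample t test on post minus pre. Two things follow.

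- **Precision.** The change score fixes the coefficient on baseline at 1. When the pre-post correlation is below 1, this carries baseline noise into the arm contrast that a fitted slope would remove.
- **Exposure to loss.** In its standard form, the ANOVA drops anyone without a post measurement. If the people lost from one arm have systematically different baseline scores, the completers in that arm regress towards the mean by a different amount, and the change contrast picks this up as an apparent effect.

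Some loss is foreseeable: training runs for 12 weeks and 36 sessions, consent can be withdrawn at any time, and participants learn their arm at the first session. Nothing in the text says that those who stop training are still invited to Visits 40 and 41. At stake is how well this small trial estimates its primary behavioural and fitness contrasts.

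**Working it through.** **1. The plan's own figure.** Inputs from the Sample Size Justification: f = 0.26, power 0.80, alpha 0.05. The pre-post correlation rho is not stated; 0.5 is assumed. For the 2 x 2 within-between interaction, lambda = f² x N x 2/(1 - rho), with 1 and N - 2 degrees of freedom. At N = 32, lambda = 0.0676 x 32 x 2/0.5 = 8.65 and power is 0.812; at N = 30 it is 0.785. The stated 32 is reproduced. The implied difference in change is 4f = 1.04 SD.

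**2. Loss rate used below.** (42 - 32)/42 = 23.8%. This is an inference, used only as a working assumption.

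**3. Precision with no loss.** With outcome SD 1 and n = 21 per arm:

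- Change score: SE = sqrt(2 x 2(1 - rho)/21)
- Baseline-adjusted, known slope: SE = sqrt(2 x (1 - rho²)/21)

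| rho | Change score | Adjusted (formula) | Adjusted (simulated) | Reduction |
|---|---|---|---|---|
| 0.3 | 0.365 | 0.294 | 0.30 | about 17% |
| 0.5 | 0.309 | 0.267 | 0.27 | about 12% |
| 0.7 | 0.239 | 0.220 | 0.22 | about 7% |

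The simulated values and reductions include the small cost of estimating the slope.

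**4. Bias from baseline-related loss, 24% lost per arm, no true effect.** If completers in one arm have mean baseline m (in SD) and the other arm's loss is random, the bias in the change contrast is -(1 - rho) x m. For a normal baseline, the lowest third has mean -1.09 and the rest +0.545.

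- *Strong pattern* (60% lost in the lowest third, 6% elsewhere): retained shares are 0.133 and 0.627, total 0.76. m = (0.133 x -1.09 + 0.627 x 0.545)/0.76 = 0.26. Bias at rho 0.3, 0.5, 0.7: -0.18, -0.13, -0.08. Simulation gives about -0.17, -0.13, -0.08, with type I error 6-7%.
- *Mild pattern* (36% and 18%): retained shares are 0.213 and 0.547. m = (0.213 x -1.09 + 0.547 x 0.545)/0.76 = 0.09. Bias about -0.06, -0.04, -0.03; simulations lie between -0.03 and -0.07, with type I error close to 5%.
- *Strong pattern in both arms, or random loss:* bias 0, type I error about 5%.

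In all of these, baseline adjustment leaves a bias of about 0 and type I error of about 5%.

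**5. Unequal loss (10 of 42 lost, rho 0.5, 4,000 simulated trials per case).** Losses are aerobic/control.

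| Loss driven by | Split | Bias, change score (SD) | Bias, adjusted (SD) |
|---|---|---|---|
| Baseline score | 8/2 | -0.21 (type I 0.10) | about 0 |
| Baseline score | 10/0 | -0.37 (type I 0.16) | about 0 |
| Partly by unseen change | 8/2 | +0.21 | +0.16 |
| Partly by unseen change | 10/0 | +0.37 | +0.28 |
| Random | 10/0 | 0 | 0 |

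The largest value is 0.37/1.04, about a third of the planning effect. The strong but balanced pattern at rho 0.5 is 0.13/1.04, about an eighth. All loss patterns are assumptions.

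**The case against.** The strongest reply is that complete-pair analysis is not biased in itself. It needs loss that depends on score differently by arm, and nothing in the documents predicts that. Both programmes are three supervised one-hour sessions a week for 12 weeks, individually tailored and progressive. The protocol also has retention measures: a bonus, regular contact, make-up sessions and homework. In the balanced patterns above, bias is small unless the loss gradient is extreme. If higher scores are better and low scorers leave the aerobic arm, the bias also works against the study hypothesis. All of this stands, so the claim is only that the contrast could be biased.

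Three stronger readings are tempting, and the documents do not support them.

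- *A reader might infer that the plan budgets for losing a quarter of participants.* No attrition rate appears. The oversampling sentence is incomplete in the available text, and 42 is also the full fMRI requirement of 21 per group, with no allowance for loss.
- *A reader might infer that poor attenders are removed from the analysis.* The availability wording concerns what a person expects. Its waiting-list option, and its listing of Visits 1 to 3, read mainly as eligibility. Applied before randomisation, it causes no arm-related bias. The attendance threshold governs only the bonus.
- *A reader might infer that a mixed model cures dropout.* It does not when loss follows unseen change, as step 5 shows.

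The reply does not answer the precision argument, which holds with no loss at all.

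**Conclusion.** The concern holds in a limited form. The stated primary behavioural and fitness test is a complete-pair change-score comparison, and a better method is available from data already being collected. The certain cost is precision, at the sizes in step 3. The conditional cost is bias. At the assumed 24% loss it runs from 0, through the mild and strong one-arm patterns in step 4, to larger values when loss is also unequal between arms. These figures rest on normal outcomes, equal variances, the assumed correlations and the assumed loss patterns. They show what could happen; the documents give no evidence that it will. The point is worth acting on because the repair is cheap, but it does not show that the planned contrast is biased.

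**What to change.** 1. Make the primary behavioural and fitness analysis a baseline-adjusted comparison of all randomised participants in their assigned arm. Use either ANCOVA on the post value or a likelihood-based mixed model with a common baseline mean. The mixed model also keeps in the baseline data of those with no post visit.
2. State that participants who stop training or miss sessions are still invited to Visits 40 and 41, unless they withdraw consent to follow-up.
3. State that the availability wording under Study Visits 4-39 applies to eligibility and does not remove anyone randomised from the analysis.
4. Report the completer ANOVA as a sensitivity analysis, together with one that allows post values to be missing not at random, since baseline adjustment does not remove bias from loss related to unseen change.

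The cost is revised analysis wording, a little more analysis work, and some effort to bring non-completers to two visits that are already planned.

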We propose to examine the effects of exercise and cardiovascular fitness on cognitive processes utilizing a parallel design randomized clinical trial. Specifically, we will investigate if exercise improves brain function in a brain area known as the entorhinal cortex. Together with the hippocampus this brain area is important for memory formation and spatial navigation. Participation in this research study will take approximately 4 months. During this time, participants will make three initial study visits. The first visit is for informed consent and screening, the second visit is for baseline fitness testing, and the third visit is for cognitive testing and a functional MRI exam. Functional MRI is a brain imaging technique that uses a magnetic field to "take pictures" of the brain while a person performs a cognitive task. It will take up to approximately three weeks to complete these initial three study visits. Following the three initial study visits, the exercise-training program will begin. Participants will be randomized to one of two training

programs: a cardiovascular endurance-training program (aerobic exercise) and a strength, balance, and flexibility training program (non-aerobic exercise). The exercise training program will last 12 weeks. There will be three one-hour exercise sessions per week. After completion of the exercise-training program, participants will attend two follow-up study visits. The first follow-up visit is for fitness testing. The second follow-up visit is for cognitive testing and an MRI exam.

Design and Procedures

Participants will be randomized into one of two groups: 1) an aerobic exercise intervention group and 2) a non-aerobic exercise control group (strength, balance, flexibility training). They will have a 50% chance to be randomized into one of the two groups.

The PI will be responsible for the randomization, because the PI's role in participant recruitment and screening is minimal. The study staff members performing the recruiting, informed consent, and screening will not know which group each participant will be randomized to at the time of recruitment, informed consent, or screening.

1) Study Visit 1: Informed Consent and Screening

Duration of Study Visit 1: Approximately 2 hours. These numbers include informed consent, general screening, breaks and neuropsychological testing. The duration of the neuropsychological testing is approx. 60-80 minutes (including breaks).

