Procedures: Procedures are identical to Study Visit 3. However, we will also include the following two neuropsychological exams, which were included at the Informed Consent and Screening Visit (Visit 1) rather than the Baseline MRI Visit (Visit 3).

Visuospatial Attention: Trail-Making Test A and B121 (baseline testing to take place during screening visit; approx. duration: 5 min)

Executive Functions: Stroop test, Victoria version121 (baseline testing during screening visit)

Procedures for Re-Screening:

Any participant who was determined eligible over three months before the exercise training program start date will need to be rescreened. The proposed timeline for eligibility and re-screening is as follows:

Eligibility timeline:

Eligibility determined at or less than 3 months before projected training start date: valid. Eligibility determined over 3 months but at or less than 12 months before projected training start date: requires phone re-screening, that will be valid for the following 3 months, detailed below.

Eligibility determined more than 12 months before projected training start date: requires a full visit Study Visit 1b (Procedures are identical to Study Visit 1) to re-assess eligibility, the will be valid for the following year.

The re-screening protocol will include a phone re-screening that consists of direct questions regarding all of the inclusion/exclusion criteria that are subject to change within 12 months or less (see attached Phone Re-Screening protocol).

After re-screening, the principal investigator and study staff member will discuss the participant's responses, and the investigator will determine whether or not the participant is still eligible for participation.

Inclusion/exclusion criteria that will NOT be directly re-screened include the following:

1. Fluent in English (must have attended elementary school and higher in English) (Inclusion Criterion #4): this cannot change from the time of initial screening to re-screening.

2. Dementia Rating Scale performance (Exclusion Criterion #4): we do not expect the participant's score to change by more than one point within the proposed 3-12-month timeline for re-screening. However, participants who originally scored a 9 on the AMSS or AEMSS at their Visit 1 will be required to come in for a full re-screening (Visit 1b) to confirm that cognitive decline has not occurred since Visit 1.

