s/he may be asked to make decisions about the presented stimuli, scenes, or environments, and to indicate responses on handheld response keys or with a joystick. Between each set of stimuli there will be a short break. We will remind the participant to keep his or her head as still as possible during task performance and the breaks in between.

We may take measurements of blood pressure, heart rate and/or pulse immediately before entering and immediately after exiting the fMRI scanner room. During fMRI scanning we may use pulse oximetry.

Outcomes

Describe anticipated primary outcome and any secondary outcomes and how they will be measured:

Primary Outcomes for Specific Aim #1:

1) Better cognitive task performance post-exercise training compared to baseline (measurements: reaction times, accuracy, etc.); effect expected to be greater for aerobic exercise training than control (strength, balance and flexibility training)

Measurements: reaction times, accuracy, and other cognitive task derived scores

2) Increased activation in and functional connectivity between brain areas associated with task performance, effect expected to be greater following aerobic exercise training than control. Measurements: blood-oxygen level dependent fMRI scans

Primary Outcomes for Specific Aim #2:

1) Better cognitive task performance post-exercise training compared to baseline (measurements: reaction times, accuracy, path length, spatial reasoning test scores, etc.); effect expected to be greater for aerobic exercise training than control (strength, balance, and flexibility training)

Measurements: reaction times, accuracy, path length, and other cognitive task derived scores

2) Increased activation in and functional connectivity between brain areas associated with task performance, effect expected to be greater for aerobic exercise training than control; this effect of aerobic exercise training will be greater for subjects with 1) smaller compared to larger relative entorhinal cortex volume, and 2) below-median compared to above median path integration skills

Measurements: blood-oxygen level dependent fMRI scans

Secondary outcomes for all aims:

1) Increased aerobic capacity for aerobic exercise group participants

Measurements: VO2max (estimated from submaximal incremental work rate test)

2) Increased strength for control group participants

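### Improvement, not an error: the primary group-by-time ANOVA is a change-score test, and ANCOVA on the baseline already collected would usually give a narrower between-arm interval

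*Combined protocol and SAP*

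**What the plan says.** - **Model.** Data Analysis, Specific Aim #1 (Behavioral and Fitness Data Analysis) makes the primary analyses "repeated-measures ANOVAs with the factors group (aerobic vs. control) and time (pre vs. post) to examine group x time interactions". For Aim #2 it states "Analyses will be as described for Specific Aim #1".
- **Scale and alpha.** The same Aim #1 paragraph adds "Dependent measures will be tested for normality and skewed data log-transformed" and "We will use an alpha of 0.05, corrected for multiple comparisons". The correction method is not named.
- **Hypothesis.** The primary outcomes of both aims begin "Better cognitive task performance post-exercise training compared to baseline", with a larger effect expected in the aerobic arm.
- **Randomisation.** Design and Procedures: "They will have a 50% chance to be randomized into one of the two groups".
- **Baseline data.** Follow-up repeats baseline. Visit 40 (fitness): "Procedures are identical to Study Visit 2". Visit 41 (MRI and cognition): "Procedures are identical to Study Visit 3". Visit 41 also repeats the Trail-Making and Stroop tests, whose baseline comes from Visit 1.
- **Covariates named.** Baseline fitness (fMRI models only), computer experience (Visit 1 screening) and motion-sickness symptoms (Visit 3, after the scan). None is the outcome's own baseline value.
- **Sample size.** 42 enrolled, 21 per arm. For cognition, the plan takes an average f of 0.26, power 0.80 and alpha 0.05 to a total of 32, oversampled to 42.

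**The concern.** With two time points, the group-by-time F statistic is the square of the t statistic comparing mean change between arms. The baseline is therefore used, but its coefficient is fixed at 1. If the true slope of the post value on the baseline is below 1, as it is whenever correlation times SD ratio is below 1, subtracting the whole baseline adds noise to the comparison. ANCOVA (post value on arm plus baseline) targets the same between-arm effect and estimates that slope from the data.

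What is at stake is precision, not validity. With 21 per arm, an interval some 10% to 20% wider than necessary is worth avoiding, because the measurements that would narrow it are already in the protocol.

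**Working it through.** **1. The plan's own figure.** Inputs from Sample Size Justification: f = 0.26, power 0.80, alpha 0.05. Neither the test family nor the pre-post correlation (rho) is stated. For a two-group, two-time within-between interaction, the noncentrality is lambda = 2 f² N/(1 - rho), with 1 and N - 2 df. At rho = 0.5 and N = 32, lambda = 2 × 0.0676 × 32/0.5 = 8.65 and power is 0.81, so 32 is reproduced. Other correlations give 44 (rho 0.3), 38 (0.4) and 26 (0.6). So rho 0.5 is the value that fits, but it remains an assumption. On this scale, f corresponds to a between-arm difference in change of 4f SD: 4 × 0.26 = 1.04 SD.

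**2. Relative precision.** Let k = post SD/pre SD. Per pre-SD², the change score has variance 1 + k² - 2 rho k, and the post value given baseline has k²(1 - rho²). Allowing for chance baseline imbalance and the lost degree of freedom:

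CI ratio (ANCOVA/planned) = sqrt[ k²(1 - rho²)/(1 + k² - 2 rho k) × (N - 3)/(N - 4) ] × t(N - 3)/t(N - 2)

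At N = 42, (N - 3)/(N - 4) = 39/38 and the t ratio is 1.0008. With rho = 0.5 and k = 1, sqrt(0.75 × 39/38) × 1.0008 = 0.878, which is 12% narrower.

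| Post/pre SD ratio (N = 42) | rho 0.3 | 0.5 | 0.7 | 0.8 | 0.9 |
|---|---|---|---|---|---|
| 0.8 | 0.718 | 0.766 | 0.803 | 0.811 | 0.791 |
| 1.0 | 0.817 | 0.878 | 0.935 | 0.962 | 0.988 |
| 1.2 | 0.885 | 0.946 | 0.997 | 1.012 | 1.002 |

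The worst case is a true slope of exactly 1 (rho × k = 1). The first fraction then equals 1, and the ratio is 1.014 at N = 42 and 1.019 at N = 32. Simulation at N = 42 (20,000 trials per setting) agreed with the table to within 0.001. It also gave null rejection of 4.7% to 5.3% for both tests, and both estimators were centred on the true effect.

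**3. Power.** Same effect scale, rho 0.5, equal SDs. For ANCOVA, lambda = 4 f² N/[(1 - rho²)(N - 3)/(N - 4)], with 1 and N - 3 df. At f = 0.26 and N = 42, lambda is 11.36 for the planned test and 11.36/(0.75 × 39/38 ) = 14.75 for ANCOVA. (The divisor is the variance ratio from step 2.) The alpha of 0.025 is illustrative, since the plan names no correction.

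| N = 42, planned to ANCOVA | alpha 0.05 | alpha 0.025 |
|---|---|---|
| f = 0.26 (plan's average) | 0.91 to 0.96 | 0.85 to 0.93 |
| f = 0.21 (visuospatial) | 0.76 to 0.86 | 0.65 to 0.78 |
| f = 0.20 (cardiovascular training only) | 0.72 to 0.82 | 0.61 to 0.73 |

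**The case against.** **This is a choice between two valid analyses.** That stands. The plan pre-specifies its model, factors and target interaction, and these match its pre-to-post hypothesis. A reader might infer that the planned test is biased or wrong. The documents do not support that: under 1:1 randomisation it is valid and unbiased.

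**The gain depends on two quantities that the plan does not give.** This also stands. The 28% figure is a corner of the grid (rho 0.3, SD ratio 0.8). The gain is about 1% at rho 0.9 with equal SDs, and nil or slightly negative at rho 0.7 to 0.9 with SD ratio 1.2. The fairest summary is the range at rho 0.5, the one value tied to the plan's N.

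**ANCOVA does not decide whether 42 is enough.** A reader might infer that it does, because at uncorrected alpha 80% power needs 48 (planned) against 38 (ANCOVA) at f = 0.21, and 52 against 40 at f = 0.20, so 42 lies between. But those are the two smallest of the five listed effect sizes, and the plan corrects alpha. At 0.025 the figures become 58 against 46 and 62 against 50, so 42 falls short either way. At f = 0.26 the planned test already exceeds 80%. The effect scale is also generous: if f means half a standardised difference (0.52 SD at f = 0.26), power at N = 42 and alpha 0.05 is only 0.38 to 0.47.

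**The match to N = 32 does not show which test was used.** A reader might infer that the trial was sized on the group-by-time test. The sample-size section names the software but no test family or correlation, so this is only an inference.

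**Some covariates are already planned.** Where computer experience and motion-sickness symptoms enter, the planned model is not a bare t-test on change. They do not free the coefficient on the outcome's own baseline, so the point remains, but the replacement model should keep them.

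**Conclusion.** The point holds as a low-cost efficiency improvement. At N = 42 and rho 0.5, ANCOVA narrows the between-arm 95% CI by 12% with equal SDs, and by 23% to 5% for SD ratios 0.8 to 1.2. Over rho 0.3 to 0.9 the range is 28% narrower to about 1% wider. The likely gain is clearly larger than the possible loss, but it is not guaranteed.

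The interval ratios assume a linear baseline slope common to both arms, complete pairs and all 42 analysed; the documents state no dropout rate. They do not depend on the effect scale. The power figures do, and they also rest on rho 0.5 and equal SDs. The voxel-wise fMRI models are outside this point.

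**What to change.** For each behavioural and fitness measure in Aims #1 and #2, pre-specify as the primary between-arm analysis a regression of the post value on assigned arm plus the same measure's baseline value. Put both values on the same scale, log-transformed where the plan's skewness rule applies. Keep the computer-experience and motion-sickness covariates where they are already planned. Report the arm coefficient with its 95% CI under the plan's multiplicity correction.

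Retain the repeated-measures ANOVA for the pre-post comparison named in the outcomes, and as a sensitivity analysis of group by time. Settle the choice before outcome data are seen by arm, so that the model cannot be selected on its result.

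The cost is a change of wording in the analysis plan, one degree of freedom, and an interval at most about 1% to 2% wider if the true baseline slope is near 1. No new data are needed.
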